2.2 Key Study End Points

The primary endpoint of the study will be the PROs, in terms of self-perceived AK symptoms and impact of AK on emotional well-being and functioning as measured using Skindex-16, at Week 8.

The secondary endpoint will be the proportion of Subjects with IGA success, defined as an IGA score of completely cleared (0) or partially cleared (1) in AK status in the treated area at Week 8.

Additional endpoints of the study will include (not exclusively):

- At Week 8, Mean satisfaction scores on TSQM-9 (effectiveness, convenience and overall satisfaction) as well as ad hoc satisfaction questions.
- At Week 8, Mean satisfaction scores on ad hoc physician satisfaction questionnaire.
- At Week 8, proportion of Subjects and Investigators rating the overall appearance of the AK treated area as ‘somewhat improved or much improved.’
- At Week 8, proportion of Subjects and Investigators reporting ‘somewhat likely or very likely’ to consider tirbanibulin in the future to retreat their AK.
- Frequency of documented adverse events (AEs), serious adverse events (SAEs) and LSRs during the first 8-weeks of the study observation period.
- Investigator rating of severity of skin photodamage at Weeks 8 and 24.
- Among Subjects with prior topical treatment experience at baseline:
 - At Week 8, proportion of Subjects and Investigators respectively rating ‘convenience/ease of use’ of tirbanibulin, and/or ‘overall satisfaction’ with tirbanibulin as ‘somewhat better or much better’ in comparison to previous topical treatments to treat their AK.
 - At Week 8, proportion of Subjects and Investigators respectively rating ‘duration of skin reactions’, ‘severity of skin reactions’ and/or ‘impact on daily activities due to skin reactions’ related to tirbanibulin, as ‘somewhat better or much better’ in comparison to previous topical treatments to treat their AK.

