5.3 Treatment Effectiveness Assessments

The effectiveness of tirbanibulin treatment will be assessed from the perspective of Site Investigators as well as the Subjects. It is expected that the Site Investigator assessments will be conducted via in-person visits/encounters at baseline, Week 8 and Week 24, and when in-person assessments are not feasible (owing to COVID-related travel restrictions), the assessments

maybe done via virtual/remote visits. The same evaluator at study site shall perform all evaluations for a subject during the study, as feasible.

5.3.1 *Investigator Global Assessment (IGA):*

Site Investigators to assess the status of subject's AK in the treated area on the face or scalp using the following IGA scale, at Weeks 8 and 24. The IGA should be representative of the investigator's overall general assessment of the subject's AK and take into account the quality, as well as the quantity, of AK lesions.

Outcome Measure	Score
Completely cleared - Approximately 100% clearance of AK lesions in the treated area	0
Partially cleared - Approximately $\geq 75\%$ clearance of AK lesions in the treated area	1
Moderately cleared - Approximately 50-74% clearance of AK lesions in the treated area	2
Minimally Cleared - Approximately <50% clearance of AK lesions in the treated area	3
Not Cleared - Approximately 0% clearance, i.e., all AK lesions remained in the treated area	4

5.3.2 *Severity of Skin Photodamage*

Site Investigators will be asked to rate the severity of skin photodamage in the AK treated area (at baseline, Weeks 8 and 24), on the following 4-point Likert scale:

Outcome Measure	Score
Absent - Smooth evenly pigmented skin	0
Mild - Freckling and/or other dyspigmentation	1
Moderate - Above plus mildly rough "dry" skin, fine wrinkling and/or telangiectasias or blotchy erythema	2

Severe - Above plus pronounced “dryness” and/or dyspigmentation and/or telangiectasia or erythema, and/or wrinkling, with or without areas of actinic purpura	3
---	---

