6.3.3 Subgroup Analysis

Primary, secondary, and additional (non-safety) endpoints may be summarized and repeated for the following subgroups, if sample size permits, using FAS:

- Gender: male and female
- Age groups: ≤ 49 years, 50-64 years, and ≥ 65 years.
- Fitzpatrick skin type: I/II, and III/IV/V/VI.
- Skin photodamage at baseline: absent/mild, moderate/severe.
- History of skin cancer: yes and no.
- AK Treatment location: face only, scalp only, both face & scalp.
- Prior treatment experience, as applicable:
 - Cryosurgery vs. all others;
 - Other topical treatments vs. all others;
 - Treatment naïve vs. all others.

Subgroup analyses based on patient retreatment status between Week-8 and Week-24 visits (Klisyri vs. other topicals vs. non topicals vs. not retreated) may be considered for relevant outcome measures, based on data availability.

Subgroup analyses will either assess the difference in outcomes within a specific strata at a given time period (for measures collected only at Week-8 and/or Week-24), or assess CFB within a specific strata (for measures collected at baseline and at Week-8 and/or week-24).

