6.6.2 Cosmetic Appearance of Skin

Subject and Site Investigator’s rating of overall appearance of the skin in the AK treated area at Weeks 8 and 24 will be respectively analyzed descriptively, and frequency of responses will be tallied for all Subjects. Proportion of respondents who indicated ‘somewhat improved or much improved’ on the response scale will be reported, using the FAS dataset.

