6.6.3 Photodamage Severity Analyses

The proportion of Subjects with a severity of score of 0 (absent) and proportion of subjects with a severity score of 0 (absent) or 1 (mild) in clinician assessment of AK-related photodamage at baseline, and at Weeks 8 and 24 will be assessed respectively. CFB in photodamage severity score at Weeks 8 and 24 will be explored and reported using descriptive statistics. This analysis will be conducted using the FAS dataset.

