7.2 Tables from Clinician's DCF (FAS Population)

Clinician data is analyzed using the FAS dataset. In relevant instances (such as IGA and physician satisfaction evaluations), only FAS dataset with corresponding week clinician data is used. All data tables in this section correspond to FAS population.

Table 2.1 Site Characteristics

Domain	(N=x)
SC1: Current workplace	
Private, office-based practice	n (%)
Hospital-based practice	n (%)
SC2: Total number of board-certified dermatologists in the practice (including yourself, if applicable)	N, Mean (SD), Median, Min, Max
SC3: At present, how many patients with AKs do you personally manage in a given month?	N, Mean (SD), Median, Min, Max
SC4: How long have you been practicing dermatology, post-residency?	N, Mean (SD), Median, Min, Max

Note: Data from Clinician DCF. The denominator for the percentage is N which refers to total number of unique sites in PROSES study.

Table 2.2 Study Subject Selection Criteria

Domain (N=X)	Yes	No
SS1r1 Diagnosed with actinic keratosis of the face and/or scalp?	n (%)	n (%)
SS1r2 Has clinically typical, visible, and discrete AK lesions?	n (%)	n (%)
SS1r3 Considered a candidate for tirbanibulin (Klisyri®) AND you plan to administer tirbanibulin (Klisyri®) treatment?	n (%)	n (%)
SS1r4 At least 18 years of age at the time of initiation of tirbanibulin (Klisyri®) treatment?	n (%)	n (%)
SS1r5 Willing to avoid excessive sun or UV exposure, and/or use relevant sunscreen protection and protective clothing during the study duration.	n (%)	n (%)
SS1r6 Able to read and write English.	n (%)	n (%)
SS1r7 Able to provide consent to participate AND is willing to comply with study procedure?	n (%)	n (%)
SS2r1 Have another dermatological condition of the face that could interfere with the actinic keratosis clinical evaluations?	n (%)	n (%)
SS2r2 Hypertrophic AK lesions, open wounds or suspected skin cancers within close proximity of the treatment area	n (%)	n (%)
SS2r3 Anticipated need for in-patient hospitalization or in-patient surgery within the next 2 months.	n (%)	n (%)
SS2r4 Have a medical chart accessible to complete baseline data collection?	n (%)	n (%)

Note: Data from Clinician DCF. The denominator for the percentage is the number of patients with available data (N=X). There are no missing data.

Table 2.3 Patient Clinical Characteristics from Medical Chart

Character	Statistics	Baseline (N=XX)
PC1 Gender		
Male	n (%)	
Female	n (%)	
Other	n (%)	
PC2 Primary Health Insurance		

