How do you rate the current severity of skin photodamage in the AK affected area?			
Responses will need to be recoded	AK4	AK8_3	AK8_3
0. Absent	n (%)	n (%)	n (%)
1. Mild	n (%)	n (%)	n (%)
2. Moderate	n (%)	n (%)	n (%)
3. Severe	n (%)	n (%)	n (%)
Absent/ Mild (0/1)	n (%)	n (%)	n (%)
Moderate/Severe (2/3)	n (%)	n (%)	n (%)
Who did the evaluation of patient's AK severity?			
1. Dermatologist	AK5	AK8_4	AK8_4
2. Nurse practitioner	n (%)	n (%)	n (%)
3. Physician's assistant	n (%)	n (%)	n (%)
How was the evaluation of AK severity done?			
1. During in-person patient visit (face-to-face)	AK6	AK8_5	AK8_5
2. Via tele-health visit (video)	n (%)	n (%)	n (%)

Table 2.8 CFB for Current Severity of Photodamage in the Original Treated Area

Domain	CFB in Proportion at Week 8 N=X (%)	p-value	CFB in Proportion at Week 24 N=X (%)	p-value
How do you rate the current severity of skin photodamage in the AK affected area?				
Absent (0)	%		%	
Mild / Moderate / Severe (1 / 2 / 3)	%	p	%	p
Absent / Mild (0 / 1)	%		%	
Moderate / Severe (2 / 3)	%	p	%	p

Table 2.9 Subgroup Analysis of Current Severity of Photodamage in the Original Treated Area

Subgroups	% Absent / Mild (0 / 1)		Baseline		Week 8		Week 24	
		n (%)		n (%)	P	n (%)	P	
Gender								
Male								
Female								
Age Group								
≤ 49 years								
50 – 64 Years								
≥ 65 years								
AK Treatment Location								
Face								
Scalp								
Both								
Fitzpatrick Skin Type								
I / II								
III / IV / V / VI								
Skin Photodamage								
Absent/mild								
Moderate/Severe								
History of Skin Cancer								
Yes								
No								
Prior Treatment Experience: Use of Cryosurgery								
Yes								
No								
Prior Treatment Experience: Use of Other Topical Treatments								
Yes								
No								
Prior Treatment Experience: Treatment Naïve at Baseline								
Yes								
No								

P-values correspond to CFB at respective time periods, within the corresponding strata.

Table 2.10 Clinician Evaluation of IGA in the Original Treated Area

Character	Week 8 (N=x)	Week 24 (N=X)
Overall, how is your patient's AK in the original treated area right now?		
Responses will need to be recoded	AK8_1	AK8_1
0. Completely Cleared	n (%)	n (%)
1. Partially Cleared	n (%)	n (%)
2. Moderately Cleared	n (%)	n (%)
3. Minimally Cleared	n (%)	n (%)
4. Not Cleared	n (%)	n (%)
(0 / 1) Completely/Partially Cleared	n (%)	n (%)
2 Moderately Cleared	n (%)	n (%)

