Table 2.35 Patient Treatment Details, If Retreated After Week 8: Clinician Reported

Domain	Week 24 (N=x)
RMH2: I started a new AK treatment for this patient within the past 16 weeks, following patient's Week-8 visit.	
RHM2 = 2 No	n (%)
RMH2Ar1: Tirbanibulin (Klisyri®)	n (%)
RMH2Ar2: Another topical treatment	n (%)
A [OTE1r1]	
RMH2Ar3: Another treatment (which is not topical)	n (%)
A [NTR1r1]	

Note: Data from Clinician DCF, from week-24.

Table 2.36 Reason for Retreatment, If Retreated with After Week 8

Domain	Statistics	Week 24			Total
		Retreated with Klisyri® (RMH2Ar1) (N=x)	Retreated with Another Topical Treatment (RMH2Ar2) (N=x)	Retreated with Non-Topical Treatment (RMH2Ar3) (N=X)	
Why was this patient re-treated?					
1. To manage newly emerged AK lesions	n (%)	RTE1_5r1	OTE1r7r1	NTR1r7r1	
2. To re-treat original* treated AK lesions	n (%)	RTE1_5r2	OTE1r7r2	NTR1r7r2	
3. Other	n (%)	[RTE1_5r3oe]	[OTE1r7r3oe]	[NTRr7r3oe]	

Note: Data from Clinician DCF, from week-24.

Table 2.37 Area of Tirbanibulin Treatment, If Retreated with After Week-8

Character	Week 24 If retreated with Klisyri® (N=x)
AK3A1: What is the AK treatment area you have identified for the patient, to apply tirbanibulin (Klisyri®)?	
Left	
Face	n (%)
Scalp	n (%)
Right	
Face	n (%)
Scalp	n (%)
Center	
Face	n (%)
Scalp	n (%)
Unknown	
Face	n (%)
Scalp	n (%)
Overall	
Face (any area)	n (%)
Scalp (any area)	n (%)

Note: Data from Clinician DCF, from week-24.

Table 2.38 Tirbanibulin Treatment Characteristics if Retreated after Week 8

Character	Week 24 If retreated with Klisyri® (N=x)
TH1B: Prescription dose	
1. 1% tirabibanibulin, single-dose packets	n (%)
2. Other, please specify [TH1Br2oe]	n (%)
a. X	
TH1C: Prescription frequency	
1. Once daily for 5 consecutive days	n (%)
2. Other, please specify: [TH1Cr2oe]	n (%)
a. X	
RTE1_4: Treatment Status	
1. Patient completed the planned treatment course	n (%)
2. Discontinued due to treatment side-effect	n (%)
3. Discontinued due to treatment intolerance	n (%)
4. Discontinued due to lack of effectiveness	n (%)
5. Discontinued due to other reasons: [RTE1_4r5oe]	n (%)
6. Don't know / Not applicable	n (%)
RTE1_5: Why was this patient re-treated	
RTE1_5r1: To manage newly emerged AK lesions	n (%)
RTE1_5r2: To re-treat original* treated AK lesions	n (%)
RTE1_5r3: Other reason: [RTE1_5r3oe]	n (%)

Note: Data from Clinician DCF, from week-24.

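### Week-24 IGA, photodamage and appearance results pool patients re-treated for their original lesions after Week 8, so they cannot show how far the first course's effect persisted

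*SAP*

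**What the plan says.** **Week-24 outcomes.** SAP 5.3.1 has the IGA scored "using the following IGA scale, at Weeks 8 and 24". The item in Table 2.10 asks about the present state of the area: "Overall, how is your patient's AK in the original treated area right now". SAP 2.2 lists "Investigator rating of severity of skin photodamage at Weeks 8 and 24" among the additional endpoints, and SAP 6.6.3 adds that "CFB in photodamage severity score at Weeks 8 and 24 will be explored and reported using descriptive statistics". SAP 6.6.2 plans a descriptive analysis of the patient's and investigator's "rating of overall appearance of the skin in the AK treated area at Weeks 8 and 24".

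**Who is in the tables.** For clinician data such as the IGA, the introduction to SAP 7.2 says that "only FAS dataset with corresponding week clinician data is used". That is a limit on data availability. No text or footnote excludes, splits or recodes re-treated patients.

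**Re-treatment.** Tables 1.28 and 2.35 count patients who started a new AK treatment between Weeks 8 and 24: tirbanibulin, another topical, or a non-topical. Table 2.36 records why, and one listed reason is "To re-treat original* treated AK lesions", coded RTE1_5r2, OTE1r7r2 and NTR1r7r2 for the three treatment types.

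**Existing provision.** SAP 6.3.3 names a four-way split by re-treatment status, but such analyses "may be considered for relevant outcome measures, based on data availability". Protocol 12.3.3 has a two-way version, also optional. The sensitivity analyses in SAP 6.9 cover missing data and visit type only.

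**The concern.** Week 24 is the only scheduled assessment after Week 8. A reader who sees a Week-24 column under a title about the original treated area will tend to take it as what remains of the first five-day course. The column does not measure that. Take a patient rated minimally cleared at Week 8, re-treated for the same lesions soon after, and clear at Week 24. That patient enters as a Week-24 IGA 0/1 in the original treated area, indistinguishable from one who cleared after the first course and stayed clear.

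The same applies to the other two measures. The study's own list of AK therapies (Table 2.30) includes photodynamic therapy, chemical or acid peel and laser, so a Week-24 photodamage or appearance rating may follow another procedure on the same skin. Photodamage is the one measure of the three that is a listed Week-24 endpoint, and Tables 2.8 and 2.9 attach change-from-baseline p-values to it.

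What is at stake is the meaning of the Week-24 results, not the study's main conclusions.

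**Working it through.** The plan states no re-treatment rate, no expected Week-24 success rate and no power calculation, so there is no figure to reproduce. The check has two parts.

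**1. Does any provision separate the re-treated patients?**

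- *Main tables* (1.10, 2.7, 2.8, 2.10, 2.13, 3.1): one Week-24 result per rater, with no re-treatment row.
- *Subgroup tables* (1.11, 2.9, 2.12, 2.14): rows for gender, age, location, skin type, photodamage, skin cancer history and prior treatment. None is for re-treatment.
- *Optional split in SAP 6.3.3*: by type of re-treatment. It does not distinguish re-treatment of original lesions from treatment of new ones.
- *Satisfaction*: here the plan does separate courses. Tables 1.29, 1.30, 2.39 and 2.40 are reserved for patients re-treated with tirbanibulin. The clinical outcomes have no equivalent.
- *Protocol 7.4*: patients also rate the appearance of a newly re-treated area. This leaves re-treated patients in the original-area item, and the SAP has no table for it.

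The pooling is therefore real for all three measures.

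**2. How large could it be for the IGA?** Among FAS patients with Week-24 clinician data, let

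- r = share re-treated for original lesions (not in the documents; assumed 5% to 30%),
- s = Week-24 IGA 0/1 rate in those patients (not in the documents; assumed 40% to 90%),
- q = Week-24 IGA 0/1 rate in the rest (assumed 60% to 75% where needed).

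Pooled rate = (1 − r)q + rs. 
Rate of success without re-treatment of original lesions, same denominator = (1 − r)q. 
Gap = rs, whatever q is.

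| r | s | Gap (points) |
|---|---|---|
| 0% | any | 0 |
| 5% | 40% | 0.05 × 0.40 = 2 |
| 10% | 60% | 0.10 × 0.60 = 6 |
| 15% | 70% | 0.15 × 0.70 = 10.5 |
| 30% | 90% | 0.30 × 0.90 = 27 |

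Example: q = 60%, r = 20%, s = 60%. Pooled = 0.80 × 0.60 + 0.20 × 0.60 = 60%. Success without re-treatment = 0.80 × 0.60 = 48%.

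For scale, the 95% half-width of a proportion with 300 patients is 1.96 × √(0.5 × 0.5 / 300) = 5.7 points at 50% and 1.96 × √(0.75 × 0.25 / 300) = 4.9 points at 75%. The SAP uses 300 for the Safety Population. The Week-24 IGA denominator cannot be larger, so the real half-width at a given proportion is at least this wide.

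**A second comparison has no fixed sign.** Against the not-re-treated patients alone, the pooled rate differs by r(s − q). With r = 30%, s = 40%, q = 75% this is 0.30 × (−0.35) = −10.5 points. With r = 30%, s = 90%, q = 60% it is 0.30 × 0.30 = +9 points. Simply dropping re-treated patients is therefore not a neutral correction.

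**The case against.** The strongest reply is that the as-observed column is a legitimate quantity. This is a descriptive, single-arm, usual-care cohort, and the state of the original area at Week 24 whatever was done in between is a reasonable thing to report. Neither document states an objective or endpoint about duration of effect. IGA success is defined at Week 8, as are the listed appearance endpoints, and that assessment comes before the re-treatment window. Tables 1.28, 2.35 and 2.36 will also let a reader see roughly how many patients were re-treated and why. All of this stands. It means the pooled column should be kept and labelled, not replaced.

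Several stronger readings are tempting and are not supported.

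- *That the Week-24 success rate is wrong by r × s.* That gap exists only against a definition counting re-treatment as non-success, which the plan never adopts, and both inputs are assumed.
- *That re-treatment turns failures into successes.* A patient partially cleared at Week 8 is already an IGA success and may still have residual lesions re-treated.
- *That all the Week-24 p-values test benefit.* In Tables 1.11, 2.12 and 2.14 they compare strata, such as male with female. Only Tables 2.8 and 2.9 test change from baseline.
- *That never-re-treated patients give the clean answer.* They are selected for not having needed re-treatment, which could flatter the initial course.

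The reply does not cover the absence of any firm analysis from which persistence of the first course could be read, although the reason codes for it are already collected.

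**Conclusion.** The point holds as a reporting gap, and closing it is a cheap improvement. As written, the Week-24 original-area results mix the initial course with later AK therapies, and the one provision is optional, has no table row and does not separate original from new lesions. The pooling itself can be confirmed from the documents; its size cannot. The 2 to 27 points rest entirely on the assumed ranges for r and s and on the comparison with success without re-treatment of original lesions. For photodamage and appearance no size is claimed. A reader might infer that the study's main results are compromised. They are not: the Skindex-16 primary endpoint and the IGA success secondary endpoint are both at Week 8.

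**What to change.** 1. Keep the as-observed Week-24 columns and label them 'regardless of re-treatment'.
2. In the Week-24 columns of Tables 2.10 and 2.12, add a row for IGA 0/1 without re-treatment of original lesions. Patients with RTE1_5r2, OTE1r7r2 or NTR1r7r2 stay in the denominator and count as not successes. Use this row for any statement about persistence of the initial course.
3. Make the SAP 6.3.3 re-treatment split mandatory for Week-24 photodamage (Tables 2.7 to 2.9) and appearance (Tables 1.10, 1.11, 2.13, 2.14, 3.1). Show re-treated and not-re-treated patients beside the pooled result, and note that the not-re-treated group is selected. Do not rest the change-from-baseline conclusion on that group alone.
4. Add a sensitivity row that also counts patients re-treated for newly emerged lesions as re-treated. The reason code identifies lesions, not area, and Table 2.37 gives the re-treated area only for Klisyri, so new lesions inside the original area cannot otherwise be ruled out.

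The cost is SAP wording and extra rows in existing shells; no new data are needed. The downsides are a Week-24 IGA figure that can only be equal or less favourable beside the as-observed one, small strata, and a sensitivity row that will sweep in some patients treated elsewhere on the face or scalp.
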